## **7. PLANNED ANALYSIS**

The format of the listings and tables will follow the BI guideline "Standards for Reporting of Clinical Trials and Project Summaries" [\(3\)](#).

[figure not shown]
Disposition of the patient population participating in the trial will be summarized by the presentation of the frequency of patients screened, screened but not entered, entered but not treated, entered and treated, who completed planned treatment period, who were prematurely discontinued from trial medication by reasons, who completed the study, and who prematurely discontinued from the study.

A frequency of patients with iPDS will be presented by treatment group for treated set. The frequency of patients in different analysis sets will also be presented for each treatment group. The iPDS per patient will be listed indicating whether the iPD led to exclusion from patient sets analysed.

For tables presenting descriptive analysis of the endpoints and other variables, the set of summary statistics is: N (number of patients with nonmissing values) / Mean / SD / Min / Q1 (lower quartile) / Median / Q3 (upper quartile) / Max.

Statistical parameters will be displayed to a defined number of decimal places as specified in the BI guideline "Reporting of Clinical Trials and Project Summaries" [\(3\)](#).

Tabulations of frequencies for categorical data will include all possible categories and will display the number of observations in a category as well as percentage (%) relative to the respective treatment group. Percentages will be based on all patients in the respective patient set whether they have non-missing values or not. Percentages will be rounded to one decimal place. The category missing will be displayed if and only if there are actual missing values.

## **7.1 DEMOGRAPHIC AND OTHER BASELINE CHARACTERISTICS**

Only descriptive statistics are planned for this section.

Descriptive statistics for demographic parameters and baseline characteristics will be presented by treatment, based on the TS.

For the continuous variables described below, categories are defined in [Table 7.1:1](#). These variables will be presented according to the number and percentage of patients in each category, in addition to the display of the summary statistics for continuous variables.

Table 7.1: 1 Categories for summary of continuous variables

Variable	Categories
Age (years)	< 50 50 to < 65 65 to < =75 >75
	< 65 ≥ 65
Weight (kg)	≤ 70 > 70 to ≤ 80 > 80 to ≤ 90 > 90
BMI (kg/m  )	< 25 25 to < 30 ≥ 30
eGFR (mL/min/1.73 m  )	≤ 30 > 30 to ≤ 45 > 45 to ≤ 60 > 45 to ≤ 60 > 60 to ≤ 90 > 90
Time since first diagnosis of (years)	≤ 1 > 1 to ≤ 5 > 5 to ≤ 10 > 10
Baseline HVPG (mmHg)	≤ 12 >12
	≤ 15 >15

## 7.2 TREATMENT COMPLIANCE

Only descriptive statistics are planned for this section of the report.

The compliance based on TS will be described as collected in the eCRF. Number and percentage of patients with compliance in following categories will be displayed at each visit since week 1:

- “Yes”,
- “No” and,
- “Missing”.

### **7.3 CONCOMITANT DISEASES AND MEDICATION**

Only descriptive statistics are planned for this section of the report. Analyses of the concomitant diseases and medication as well as non-drug therapies will be based on TS.

Concomitant diseases will be coded according to the most recent version of Medical Dictionary for Drug Regulatory Activities (MedDRA).

Concomitant medication will be coded according to the most recent version of the World Health Organisation – Drug Dictionary (WHO-DD).

A medication/non-drug therapy will be considered concomitant to treatment if it:

- is ongoing at the start of trial medication intake
- starts within the on-treatment period (see [Section 6.1](#) for a definition of study analysis phases).

Concomitant medication use will be summarised with frequency and percentage of patients by Anatomical Therapeutic Chemical 3 (ATC3) class and preferred name.

### **7.4 PRIMARY OBJECTIVE ANALYSIS**

The primary endpoint for this study is the percentage change from baseline in HVPG from baseline after 8 weeks of treatment.

#### **7.4.1 Main analysis**

For the primary endpoint, the analysis of covariance (ANCOVA) will be used. The analysis will be performed on the FAS and include on-treatment HVPG only. If a patient misses the Week 8 visit, the missing data will not be imputed.

[figure not shown]
The statistical model will be:

Percentage HVPG change from baseline at Week 8 = overall mean + HVPG baseline + treatment + random error

This model includes treatment as fixed classification effects and baseline HVPG as a linear covariate. The random error is assumed to be normally distributed with mean 0 and variance  $\sigma^2$ . The analysis will only be used for estimation of treatment effects without performing statistical tests.

The main analysis will implement the primary estimand defined in [Section 6.3](#) and be performed on FAS. All data collected after the intercurrent events will be used for the analysis. The number of patients reporting each type of intercurrent event will be summarized for overall and each treatment group.

If after all the steps above have been investigated without successful model convergence, then an ANCOVA (Analysis of Covariance) model at Week 8 only, will be performed. If the above sequence of methods does not lead to convergence for a particular subgroup, then that analysis will not be performed or reported.

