## **2. TRIAL OBJECTIVES AND ENDPOINTS**

### **2.1 MAIN OBJECTIVES, PRIMARY AND SECONDARY ENDPOINTS**

#### **2.1.1 Main objectives**

The trial will investigate the safety and tolerability of BI 685509 in patients with CSPH in compensated cirrhosis due to HBV, HCV and NASH with or without T2DM and the combination of BI 685509 and empagliflozin in patients with CSPH in compensated cirrhosis due to NASH with T2DM, on top of standard of care respectively. The primary objective is to estimate the percentage change in HVPG from baseline measured after 8 weeks. The primary analysis will be made for treated patients with baseline HVPG measurements (Full Analysis Set, FAS) as if all patients took treatment for the duration of the trial.

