## **7.2.2 Handling of intercurrent events**

The expected intercurrent events of interest in this trial are:

- use of the following restricted concomitant therapy:
  - NO-sGC-cGMP pathway activating therapies like NO-donors (e.g. glyceryl trinitrate, isosorbide di- or mono-nitrate, molsidomine), PDE-5-inhibitors (e.g. sildenafil, tadalafil, and vardenafil), non-specific PDE inhibitors such as dipyridamole and theophylline, or sGC-stimulators (e.g. riociguat)
- new onset of / dose change in existing NSBB / carvedilol, pioglitazone, GLP1-agonists and vitamin E concomitant therapy
- occurrence of a decompensation event
- Premature discontinuation of assigned trial medication

The strategies for handling intercurrent events in this trial are as follows:

Treatment Policy: This is the effect of randomizing patients to a treatment arm regardless of treatment actually being taken. All intercurrent events will be handled according to the treatment policy approach as defined in ICH E9(R1).

Each analysis will reference the strategy for handling intercurrent events that it will be estimating. The estimand for each main analysis in this protocol is the combination of the relevant detailed clinical objective from [Section 2.1](#) and this strategy.

Handling of the intercurrent events that are not listed above will be decided by the review and will be documented in the TSAP.

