### 7.2.3 Primary objective analyses

The primary endpoint (refer to [Section 2.1.2](#)) will be analyzed using an ANCOVA model in the FAS without imputing the missing data.

The model is as follows:

Percentage of HVPG change from baseline at Week 8 = overall mean  
+ HVPG baseline  
+ treatment  
+ random error

This model includes effects accounting for the following sources of variation: ‘treatment’ is a fixed classification effect, and ‘HVPG at baseline’ is a linear covariate. The random error is assumed to be normally distributed with mean 0 and unknown variance  $\sigma^2$ .

The analysis will only be used for estimation of treatment effects without performing statistical tests. Patients will be analysed according to the stratum to which they belong (regardless of any mis-assignment to treatment based on identification of the wrong stratum), as such an error occurs before randomisation and is therefore consistent with regulatory guidance. Procedures to follow if the analysis fails to converge will be described in the TSAP.

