**4. CHANGES IN THE PLANNED ANALYSIS OF THE STUDY**

There are no changes in this TSAP compared to the statistical methods described in the CTP.

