### **6.3 INTERCURRENT EVENTS**

The expected intercurrent events (ICEs) of interest in this trial are:

- Use of the following restricted concomitant therapy:
  - NO-sGC-cGMP pathway activating therapies like NO-donors (e.g. glyceryl trinitrate, isosorbide di- or mono-nitrate, molsidomine), PDE-5-inhibitors (e.g. sildenafil, tadalafil, and vardenafil), non-specific PDE inhibitors such as dipyridamole and theophylline, or sGC-stimulators (e.g., riociguat)
- New onset of / dose change in existing NSBB / carvedilol, pioglitazone, GLP1-agonists and vitamin E concomitant therapy
- Occurrence of a decompensation event
- Premature discontinuation of assigned trial medication

[figure not shown]
The strategies for handling those intercurrent events in this trial are as follows:

Treatment Policy: This is the effect of randomizing patients to a treatment arm regardless of treatment actually being taken. All intercurrent events will be handled according to the treatment policy approach as defined in ICH E9(R1). This will be used as the **primary strategy** of implementing the Estimand Concept (EC).

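### For premature discontinuation, SAP 7.4.1 claims treatment policy but limits the primary ANCOVA to on-treatment HVPG

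*SAP*

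**What the plan says.** **Declared estimand.** Protocol 7.2.2 and SAP 6.3 list premature discontinuation of trial medication as an intercurrent event, beside decompensation, restricted co-medication and changes in background therapy. Both assign treatment policy to every listed event. SAP 6.3 describes it so: "This is the effect of randomizing patients to a treatment arm regardless of treatment actually being taken".

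**Main analysis.** SAP 7.4.1 contains three statements that bear on this:
- "The analysis will be performed on the FAS and include on-treatment HVPG only"
- "The main analysis will implement the primary estimand defined in" Section 6.3
- "All data collected after the intercurrent events will be used for the analysis"

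**Meaning of on-treatment.** SAP 6.1 and Table 6.7:1 count HVPG as on-treatment up to 8 days after the last intake. SAP 6.7 classes anything later as post-treatment.

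**Protocol.** Section 7.2.3 says that the primary endpoint "will be analyzed using an ANCOVA model in the FAS without imputing the missing data" and does not limit it to on-treatment values. SAP section 4 states: "There are no changes in this TSAP compared to the statistical methods described in the CTP". Protocol 2.1.1 frames the primary analysis "as if all patients took treatment for the duration of the trial", which is the language of a hypothetical strategy.

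**The concern.** Under treatment policy, a Week 8 HVPG from a patient who has stopped the drug belongs in the analysis. Under the on-treatment restriction, it is left out once more than 8 days have passed since the last dose. SAP 7.4.1 asks for both, so a programmer who meets such a value has no rule to follow. The choice would then be made with the data in hand, in an open-label trial.

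Decompensation is drawn in, because protocol 3.3.4.1 requires trial treatment to stop after an acute decompensation event. For the other listed events there is no conflict while the patient stays on drug, since the HVPG after the event is still on-treatment.

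The trial tests no hypothesis. Estimating the HVPG change is nevertheless its primary objective, and protocol 1.3 and 3.2 plan an indirect comparison with trial 1366-0021. A reader of that comparison needs to know how discontinuation was handled.

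**Working it through.** **1. The 8-day allowance.** Inputs: EoT planned on Day 57 (Flow Chart); last BI 685509 dose the evening before, so Day 56 (protocol 4.1.4); HVPG allowed within seven days of the EoT visit (protocol 5.1.1). Latest allowed HVPG: 57 + 7 = Day 64. On-treatment limit: 56 + 8 = Day 64. The two agree, so the allowance does what SAP 6.1 says: it keeps delayed EoT measurements of patients who completed treatment.

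**2. What it does to patients who stop early.** In Table 6.7:2 the extended Week 8 window opens on Day 51 and closes at the medication stop date + 8 for HVPG.
- Earliest last dose that can give any on-treatment Week 8 value: 51 − 8 = Day 43.
- Earliest last dose for which a Day 57 value counts: 57 − 8 = Day 49.

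| Last dose | On-treatment Week 8 HVPG |
|---|---|
| Day 42 or earlier | none possible (limit is Day 50 or earlier) |
| Day 43 to 48 | only if measured from Day 51 to last dose + 8 (Day 56 at the latest) |
| Day 49 or later | a Day 57 value counts |

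**3. Can an excluded value exist?** Usually not. The ED visit replaces the planned visit (Flow Chart footnote 3), HVPG is not required there (protocol 6.2.2.1), and none is scheduled at EoS. But the possibility is open:
- Protocol 3.3.4 and 3.3.4.1 ask patients off treatment to attend the remaining visits.
- Protocol Appendix 10.2 sends patients stopped for liver enzymes to the EoT procedures after resolution or stabilisation.
- Footnote A of SAP Table 6.7:2 foresees off-treatment measurements and assigns them to visits in the same way as the others. The Week 12/EoS row of the same table, however, starts the day after the stop date + 8. A Day 57 HVPG after a stop on Day 40 (40 + 8 = 48) could therefore be taken as Week 8 or as Week 12.

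**4. The passages together.** If the restriction carries out the hypothetical wording of protocol 2.1.1, it contradicts protocol 7.2.2. If 7.2.2 governs, the restriction departs from protocol 7.2.3 and SAP section 4 does not declare it.

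**5. Illustration of size.** From protocol 7.5: mean reduction 20%, SD 25%, n = 20. The standard error of an arm mean is 25/√20 = 5.59 points, and Φ((20 − 10)/5.59) = 96.3%, which matches the protocol's figure. That figure does not depend on this point.

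Assumptions, none of them in the documents: 20% is the on-treatment mean; a share d of 5% to 20% stops early (1 to 4 of 20); a share q of these has a Week 8 HVPG more than 8 days after the last dose and the rest have none; their mean reduction m is 0 or 10.

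Values discarded per arm = 20·d·q. Shift in the mean = [d·q/(1 − d + d·q)]·(20 − m).

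| q | Values discarded | Shift, m = 0 | Shift, m = 10 |
|---|---|---|---|
| 0% | 0 | 0 | 0 |
| 25% | 0.25 to 1 | 0.26 to 1.18 | 0.13 to 0.59 |
| 50% | 0.5 to 2 | 0.51 to 2.22 | 0.26 to 1.11 |

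Given step 3, the low end of q is the more plausible.

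**The case against.** The best defence is that the clause is only a visit-window rule. The endpoint is the change after 8 weeks of treatment, and step 1 confirms that the 8 days were chosen to keep delayed EoT measurements. On that reading nothing has changed from the protocol. This explains the allowance. It does not explain a restriction to on-treatment values *only*, placed in the same section as an instruction to use all data after intercurrent events.

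A second defence is redaction. SAP entries between 7.4.1 and 7.4.4 are hidden, and naming treatment policy the primary strategy leaves room for another one. Hidden text may hold a sensitivity analysis, but it cannot make two visible sentences agree.

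Other objections stand, and they limit the point. A reader might infer that all early stoppers are left out; the table in step 2 shows that they are not. A reader might also count every early stopper without a Week 8 HVPG as proof of a wrong label. An HVPG never measured is missing data, which both documents openly leave unimputed; that does not itself change the declared target and is not part of this conflict.

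**Conclusion.** The contradiction is real and confined to premature discontinuation, including stops required by decompensation. It affects patients with an HVPG taken more than 8 days after the last dose. The cut-offs of Day 43 and Day 49 follow from the SAP's own tables and need no assumption.

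The number of values affected is probably small and may be zero. A reader might infer that the primary estimate is biased, or inflated by several points. With the same assumed inputs, the two estimands would differ by d·(20 − m), from 0.05 × 10 = 0.5 to 0.20 × 20 = 4 points. But that is a gap between two targets under assumed inputs, and most of it would come from HVPG never measured. The documents give no discontinuation rate, no off-drug mean and no measured share, so neither size nor direction of bias is established. The assumed effect of the filter itself, 0 to 2.2 points, lies below the 5.59-point standard error.

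This should be fixed because the main analysis of the primary endpoint cannot be programmed as written for these patients and the remedy is cheap. It is a correction of wording and does not undermine the trial.

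**What to change.** **Preferred, in the SAP:** keep the declared treatment policy.
- Delete the clause in 7.4.1 that limits the analysis to on-treatment HVPG.
- Assign Week 8 HVPG by study day whatever the medication stop date: for example from Day 51, closest to Day 57, with a stated upper limit. The limit should not fall before Day 69 (57 + 5 days of visit window + 7 days for the HVPG), or patients measured within the protocol's allowances would be lost. The SAP's midpoint convention, carried on to EoS, would give (57 + 85)/2 = Day 71.
- Keep the on-treatment version as a supplementary analysis.
- Report the number per group without a Week 8 HVPG beside the estimate.

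**Alternative:** keep the restriction, stop labelling it treatment policy for discontinuation, limit the all-data sentence to the other intercurrent events, and record the restriction as a change in SAP section 4.

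**In either case:** state in the SAP whether protocol 2.1.1 or 7.2.2 governs, and align the protocol text at the next amendment. Amendments need ethics and authority approval (protocol 8.1), so this need not prompt one by itself.

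**Cost:** a revised SAP. The preferred option adds one supplementary ANCOVA; SAP 7 and 7.4.1 already plan most of the counts. The alternative needs no new analysis. Neither needs new data, and neither recovers HVPG that was never measured.

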#### **7.4.4      Supplementary analysis**

For primary endpoint, the analysis in [Section 7.4.1](#) will be repeated in

- FAS excluding patients with down-titration or dose-interruption

### **7.5            SECONDARY OBJECTIVE ANALYSIS**

#### **7.5.1        Key secondary objective analysis**

This section is not applicable as no key secondary endpoint has been specified in the protocol.

#### **7.5.2        Subgroup analysis**

No subgroup analyses are planned for the analysis.

#### **7.5.3        Secondary objective analysis**

The secondary endpoints for this study are described in CTP Section 2.1.3.

For the occurrence of CTCAE grade 3 (or higher) hypotension or syncope based on Investigator judgement and the occurrence of discontinuation due to hypotension or syncope,

[figure not shown]
the numbers and percentages of patients with those events will be presented jointly and also separately.

For the occurrence of decompensation events, categories are defined in [Table 7.5.3:1](#).

Table 7.5.3:1 Categories for decompensation events

Categories	Scope	Definition
Acites		PT - 'Ascites' PT - 'Bacterascites' PT - 'Haemorrhagic ascites'
Variceal haemorrhage	Narrow Narrow Narrow  Broad Broad Broad	PT - 'Oesophageal varices haemorrhage' PT - 'Oesophageal haemorrhage' PT - 'Bleeding varicose vein'  HLT - 'Gastric and oesophageal haemorrhages' HLT - 'Non-site specific gastrointestinal haemorrhages'
Hepatic encephalopathy	Narrow Narrow Broad Broad	PT - 'Hepatic encephalopathy' PT - 'Coma hepatic' PT - 'Hyperammonaemic encephalopathy' PT - 'Hyperammonaemic crisis'
Other		PT - 'Cardiohepatic syndrome' PT - 'Hepatorenal syndrome' PT - 'Hepatorenal failure' PT - 'Hepatic hydrothorax' PT - 'Hepatopulmonary syndrome'

For all the secondary endpoints, only descriptive statistics will be presented.

## **7.7 EXTENT OF EXPOSURE**

A descriptive statistics table with mean, SD, median and range of the number of days a patient was on treatment will be provided for the treated set. The tables will also provide the sum total of the time that all patients pooled together were on treatment. A separate listing will be created for patients who switched treatment, had dose interruption or dose down-titration any time indicating exposure to each treatment.

A frequency table of number and percent of patients belonging to each categorical range of exposure weeks will be provided as well. The following are the categories of exposure-ranges (in weeks): “0 to 4 weeks”; “> 4 to 8 weeks” and “>8 weeks”.

No temporary treatment interruption period will be reported.

## **7.8 SAFETY ANALYSIS**

All safety analyses will be performed based on the TS following BI standards. Additionally, AE reported to be related to study procedures will be listed based on the SCR.

### **7.8.1 Laboratory data**

The analyses of laboratory parameters will be descriptive in nature and will be based on BI standards (7). Note that data from the central Laboratory will be used for all displays described below, unless otherwise specified.

For continuous safety laboratory parameters standardized and normalized values will be derived as well as the differences to baseline. Normalisation means transformation to a standard unit and to a standard reference range. The process of normalisation, handling of repeat values at the same visit for by-visit displays, as well as standard analyses for safety laboratory data are described in the BI guidance for “Handling, Display and Analysis of Laboratory Data” (7). All analyses considering multiple times of the ULN (as described below) will be based on standardised and not normalised values.

Laboratory parameters will be shown in conventional units. Where conventional units differ from SI units, analyses will be repeated on SI units in the appendix.

Laboratory values will be compared to their reference ranges and frequency tables will be provided for the number of patients within and outside the reference range at baseline and the last measurement on treatment. Descriptive statistics will be provided by treatment group and total for baseline, last value on-treatment and for changes from baseline to last value on treatment. Frequency tables will summarise the number of patients with potentially clinically significant abnormalities.

Both on-treatment and post-treatment values of the following lab parameters will be presented graphically. The values after the treatment period will be assigned to the follow-up (EoS) period.

- Haematocrit
- Haemoglobin
- RBC count / erythrocytes
- WBC / leukocytes
- Platelet count / thrombocytes
- Reticulocytes
- INR
- ALT
- Alkaline phosphatase
- AST
- Bilirubin (total)
- Albumin
- gamma-GT
- eGFR

Only patients with at least one available on-treatment value will be included in the analysis of an individual laboratory parameter. All individual data will be presented in listings.

To support analyses of liver related adverse drug effects, the frequency of patients with AST and/or ALT  $\geq$  3xULN combined with the total bilirubin  $\geq$  2xULN in a 30-day period after AST/ALT elevation will be displayed, stratified by alkaline phosphatase  $<$  2xULN and  $\geq$  2xULN (a patient can potentially be in both alkaline phosphatase strata in case of multiple AST/ALT and bilirubin elevations). The start of the 30-day time span is triggered by each liver enzyme elevation above defined thresholds. This analysis will be based on standardised laboratory values.

A graphical analysis of the ALT and total bilirubin during the on-treatment period will also be performed; the so called eDISH plot. In the graph, for each subject, the peak total bilirubin is presented as a fold increase over the ULN against the peak ALT as a fold increase over the ULN, on a log 10 scale. The measurements displayed for total bilirubin and ALT may, or may not, occur on the same date. Two reference lines, 2xULN for total bilirubin and 3xULN for ALT, are drawn onto the graph to divide the plane into four quadrants. Normal cases are in the lower left quadrant, potential DILI cases are in the upper right quadrant (Hy's Law quadrant), while the lower right quadrant is known as the Temple's corollary range (ALT  $\geq$  3xULN and total bilirubin  $<$  2xULN). The same graphical analysis will be performed for AST and total bilirubin during the on-treatment period as well. Details on patients with elevated liver enzymes will be listed.

Clinically relevant findings in laboratory data will be reported as baseline conditions (at screening) or as AEs (during the trial). If judged clinically relevant by the investigator and will be analysed as such.

